14.4 Power and Sample Size

This trial is powered to detect differences in the progression-free ratio for those with actionable mutations identified by NGS results and then treated with a targeted therapy. A hypothesized PFS ratio larger than 1.3 would suggest that the targeted therapy is doing better than the previous treatment received (not targeted), and we assume a null hypothesis PFS ratio of 1.0 (no difference). Using pilot data seen in Von Hoff et al, we assume a conservative standard deviation of 1.71. With 269 evaluable participants, we have 80% power to detect differences in PFS ratio from 1.0 to 1.3, assuming a two-sided Wilcoxon test with level of significance equal to 0.05. This does assume the actual underlying distribution is normal, but powers for a non-parametric Wilcoxon test. ("PASS 16 Power Analysis and Sample Size Software," 2018) As those that die before progression or are lost to follow-up will be non-evaluable for the primary objective, we conservatively allow for 20% non-evaluable. Therefore, we plan to recruit 337 total patients in this trial.

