1.0 Introduction and Background

Precision medicine is a rapidly growing field with the potential to bypass ineffective treatments and target specific genetic mutations present in cancer cells. Although clinicians have access to increasing amounts of data regarding tumor genomics, it can be problematic to identify a primary driver mutation and the optimal treatment.(Paolillo, Londin, & Fortina, 2016). Due to this complexity many clinicians are uncomfortable interpreting genomic sequencing results from next generation sequencing assays (“NGS”) [J. Clin Oncol 2014, 32, 1317-1323]. A recent survey of providers at a major academic center revealed that more than half the providers were uncomfortable interpreting the information from a genomic test [Oncotarget 2017; 8; 27145-27154]. Various strategies have been used to facilitate the proper interpretation of genomic data including in-person and virtual molecular tumor boards but the limited experience and large numbers of permutations with multiple genetic mutations in a single tumor make the identification of one or more driver mutations in a particular patient largely a matter of an educated guess at best. This has the effect of discouraging the use of targeted therapies, that may provide benefit, in patients who have exhausted standard of care treatments. Frequently, physicians prescribe medications off-label in an effort to delay progression of disease. Off label prescribing involves prescribing a medication for an indication other than the condition for which there is FDA approval.Those physicians prescribing targeted therapies off label, based on NGS results face other challenges. These include lack of access to available drugs, costs of available drugs, and differing reimbursement policies among insurance companies, among others (Messner et al., 2016)

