2.0 Objectives

2.1 Primary Objective

- 2.1.1 To estimate the progression-free ratio, as defined by the progression-free survival time on study treatment divided by the progression-free survival time on the last treatment received by patient, for an identified actionable mutation, who will be treated with an off-label treatment off label therapy based on a simplified selection methodology using the NGS results.

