2.3 Exploratory Objectives

- 2.3.1 To describe health related quality of life in patients undergoing off-label treatment targeting genetic mutations, as measured by the PROMIS-29 Overall Health-Related Quality of Life, Including 4-Item Anxiety Subscale..
- 2.3.2 Using the Satisfaction with Medical Decision Scale, to describe patient satisfaction with decision to pursue off-label treatment.
- 2.3.3 To identify types of actionable mutations with available targeted treatment occurring in cancer patients.
- 2.3.4 To characterize the historical treatment regimens for these patients relative to the targetable mutation.

ClinicalTrials.gov: NCT04111107

- 2.3.5 To describe patient clinical and demographic characteristics of those with actionable mutations based on NGS results.
- 2.3.6 To identify barriers to treatment based on NGS results.

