3.0 Patient Selection

3.1 Inclusion Criteria

- 3.1.1 Cancer patients at Wake Forest Baptist Comprehensive Cancer Center and its satellites who have next generation DNA sequencing results on their tumor biopsy or surgically resected tissue and/or blood samples and/or consent to the WFCCC Precision Oncology Registry to use their information for research.
- 3.1.2 Actionable mutation (defined as a mutation or gene amplification for which an off-label therapy is identified on the patient's NGS report for which NCCN guidelines do not recommend a specific treatment in the particular disease or for which there is no documentation in the patient's medical record of clinical data demonstrating lack of activity with the targeting of the specific mutation or amplification in the patient's specific disease) uncovered by the genomic sequencing of a tumor or those that have undergone liquid biopsy assay of their tumor genomic, performed by Wake Forest or another and who are medically able to receive targeted therapy based on those results.
- 3.1.3 Sequencing on a sample collected within 3 months prior to registration is strongly encouraged but must have been performed within the 12 months prior to registration.
- 3.1.4 Patients must have progressed through at least two lines of treatment, or are not candidates for or unwilling to receive any standard therapies. Patients who have received treatment on the present protocol who have progression of disease may be recruited to the trial for treatment using another targeted therapy provided that they fullfil the other criteria for participation in the trial. If a patient discontinues treatment on this protocol they can be considered for further participation in this trial provided they meet all of the eligibility criteria and are eligible for re-registration and re-consent.
- 3.1.5 ECOG of ≤ 3
- 3.1.6 Life expectancy of greater than 6 weeks

ClinicalTrials.gov: NCT04111107

3.1.7 The effects of the drugs used for cancer treatment on the developing human fetus are unknown. For this reason and because of the possibility that the agents are teratogenic, women of child-bearing potential and men must agree to use adequate contraception (hormonal or barrier method of birth control; abstinence) prior to study entry and for the duration of study participation. Should a woman become pregnant or suspect she is pregnant while participating in this study, she should inform her treating physician immediately.

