14.2 Analysis of Primary Objective

The primary objective of this non-randomized, single-arm pragmatic trial is to estimate the progression-free ratio as defined by the duration of time from start of treatment to the time of progression divided by the duration of time from the last treatment received pre-trial to the time of progression on that treatment. Those that die before progression or are lost to follow-up will be non-evaluable for the primary objective. The median progression-free ratio will be estimated with the range and a two-sided Wilcoxon Signed Rank test will be calculated to see if the PFS ratio is different from 1.0.

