14.3 Analysis of Secondary and Exploratory Objectives

Response rate will be estimated for all patients with corresponding 95% confidence intervals. Progression-free survival and overall survival times will be displayed using Kaplan-Meier curves with median survival times and confidence intervals. Adverse events will be summarized in incidence tables by type and grade severity for all patients and presented by type of treatment received. For exploratory objectives, the frequency of types of actionable mutations and previous treatment history will be summarized and demographic characteristics presented. Logistic models will be constructed for each type of mutation (yes/no) to preliminarily explore associations with clinical and demographic characteristics. For quality of life and patient satisfaction outcomes, changes over time will be assessed using a repeated measures ANOVA, with any between time associations utilizing Tukey adjustment for post-hoc comparisons. Transformations and/or non-parametric approaches will be considered for any outcomes violating parametric assumptions.

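### Section 6.0 step 7 does not stop a patient from being assigned a listed drug on which they have already progressed

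*Combined protocol and SAP*

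**What the plan says.** **Drug selection (Section 6.0, steps 6 and 7, and flow chart).** Each patient receives a random Treatment Number from 1 to 6. Once a mutation is selected, and if the report lists several drugs for it, the number picks the drug. Step 7 moves to the next listed drug in two situations: a contraindication according to the label, or a drug that cannot be obtained. It repeats this until something suitable is found, then goes to the next actionable mutation, and asks for documentation of why drugs were passed over. The flow chart gives the same two reasons.

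**Eligibility (Section 3.1).** Section 3.1.2 defines an actionable mutation as one with an off-label therapy on the report "for which NCCN guidelines do not recommend a specific treatment in the particular disease or for which there is no documentation" in the patient's record of data showing that targeting it lacks activity in that disease. Section 3.1.4 says that patients who progress on this protocol "may be recruited to the trial for treatment using another targeted therapy".

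**Primary endpoint.** Section 2.1.1 has progression-free time on study treatment "divided by the progression-free survival time on the last treatment received by patient". Section 14.2 has time to progression on study treatment "divided by the duration of time from the last treatment received pre-trial to the time of progression on that treatment". Neither limits the type of that last treatment. Section 14.4 nevertheless reads a ratio above 1.3 as suggesting that "the targeted therapy is doing better than the previous treatment received (not targeted".

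**The concern.** These patients have mostly had at least two lines of treatment, and some may already have taken a drug that their sequencing report lists. The protocol assigns by random number, and Section 4.0 has the registrar assign the drug and dose. A safeguard that is not in the rule therefore depends on someone stepping outside it. Followed exactly, the rule can give a patient with advanced cancer a drug that has already failed, while other listed drugs or mutations have not been tried.

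The endpoint is affected too. If the failed drug was the last line, numerator and denominator are two courses of one drug. That patient's ratio says nothing about whether assignment from sequencing improves on what came before.

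**Working it through.** **1. Does any provision block reassignment?**

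| Provision | What it covers | Does it close the gap? |
|---|---|---|
| Step 7 and flow chart | Contraindicated, or not obtainable | No. Prior progression is neither |
| 3.1.2, first alternative | No NCCN-recommended treatment in the disease | No. It ignores the patient's drug history |
| 3.1.2, second alternative | No record of data showing lack of activity when the mutation is targeted in that disease | In part. It is joined to the first by an 'or', so a mutation can qualify without it. It acts on mutations, not drugs, and does not clearly cover a drug that worked and then failed |
| 3.1.4 | A different targeted therapy on re-entry after progression on this protocol | In part. It covers re-entry only, and step 7 has no matching rule |
| Appendix A checklist | Repeats the criteria of Section 3 | No item on prior progression on a listed drug |

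The remaining case is a patient who progressed, outside this protocol, on a drug listed for the selected mutation. Section 3.1.2 requires an off-label therapy on the report, so this is mainly earlier off-label use of the same drug.

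**2. Chance that the failed drug is selected first.** This is conditional on the drug being listed for the selected mutation. Let k be the number of listed drugs, and assume Treatment Numbers 1 to 6 are equally likely.

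- k = 1: 100%; no number is needed.
- k = 6: 1/6 = 17% for each drug.
- k = 2 to 5: step 7 has no rule for a number larger than k, so any figure needs an assumption.
  - If the last listed drug is taken, as step 4 does for mutations, that drug has 5/6, 4/6, 3/6 and 2/6 (83%, 67%, 50%, 33%) for k = 2, 3, 4, 5. Every other drug has 1/6 (17%).
  - If the count returns to the top, each drug has 50% for k = 2 and 33% for k = 3. For k = 4, the first two have 33% and the others 17%. For k = 5, the first has 33% and the others 17%.

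The Schema gives treatment levels 1 to 4 rather than 1 to 6. On that range, with four drugs listed, each has 1/4 = 25%.

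These are chances of first selection, and they do not bound eventual assignment from below. A drug selected first can still be dropped as contraindicated or unobtainable. One not selected first can be reached later when others are dropped.

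**3. Is the sample size touched?** Inputs from Section 14.4: difference 0.3, SD 1.71, two-sided 0.05, power 80%, 20% non-evaluable.

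- Normal approximation: (1.71 × (1.960 + 0.842) / 0.3)² = 255.0. With the noncentral t, 257.
- Wilcoxon efficiency under normality: 257 × π/3 = 269.1, against the stated 269. Power at 269 is 79.99%.
- Recruitment: 269 / 0.80 = 336.25, so 337, as stated.

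None of these inputs depends on step 7 or on the parenthetical in Section 14.4.

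**The case against.** The best defence is that the gap is narrow and clinically policed. The pool is meant to be off-label therapy, so a standard on-label drug that failed is largely outside it. A patient's own progression, if recorded, could arguably count under the second alternative of 3.1.2. Step 7 looks for a suitable drug, and the treating physician signs the eligibility checklist.

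The narrowing stands, and the point is confined to it. The rest does not close the gap. The search for a suitable drug starts only after one of the two named reasons, and the 3.1.2 safeguard remains optional because of the 'or'.

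On Section 14.4, the defence is right that nothing operative follows. Section 14.2 tests only whether the ratio differs from 1.0, and Section 14.1 describes the aim as evaluating an approach to assigning treatment.

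A reader might still infer that targeted last lines are common, or that they cost the trial power. The documents support neither. Section 1.0 says "Frequently, physicians prescribe medications off-label in an effort to delay progression of disease", but that concerns medications generally, and the same section says that genomic complexity discourages targeted therapy. No share of targeted last lines is given, and nothing fixes the ratio at 1.0 after one. Nor does re-entry prove the parenthetical wrong: Section 14.2 refers to the last pre-trial treatment, so protocol therapy need not become a re-entrant's denominator, although Section 2.1.1 is looser.

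**Conclusion.** The gap in step 7 is real on the text and worth closing. It concerns patients who progressed outside this protocol on a drug listed for the selected mutation. For them, first selection of that drug ranges from 17% with six listed drugs to 100% with one, given equally likely numbers from 1 to 6. How many such patients there will be is not stated, so neither the number exposed nor the effect on the median ratio can be sized. It would go too far to read the percentages as the share of patients who would receive a failed drug.

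The Section 14.4 parenthetical is an editorial slip. The ratio supports only a comparison with the last treatment received. The primary test, the estimate, 269 evaluable and 337 recruited all stand.

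**What to change.** In step 7 and the flow chart, add a third reason for moving to the next listed drug: *or the patient has previously progressed on the selected drug*. If the list for that mutation runs out, the existing rule already moves to the next actionable mutation. Record the reason in the documentation that step 7 already requires. The same clause gives 3.1.4 the matching selection rule that it lacks.

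The cost is two short edits, plus having the treatment history to hand when the drug is assigned; Section 5.3 already collects it. A few patients will move off the randomly numbered drug. A patient with no other suitable listed drug could not be treated on protocol.

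Separately, delete the two-word parenthetical in Section 14.4 and refer to the last treatment received. Endpoint, test and sample size do not change.

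### The 80% power in section 14.4 is computed for a normally distributed PFS ratio; a ratio of two durations with SD 1.71 cannot be normal, so the stated power is not supported for this endpoint

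*Combined protocol and SAP*

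**What the plan says.** Section 14.2 defines the primary endpoint as time to progression on study treatment divided by time to progression on the last pre-trial treatment. On the summary it says "The median progression-free ratio will be estimated with the range", and it adds a two-sided signed-rank test of the ratio against 1.0. It mentions no transformation.

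Section 14.4 gives the sample size: "With 269 evaluable participants, we have 80% power to detect differences in PFS ratio from 1.0 to 1.3". The test behind that figure is a Wilcoxon test, two-sided at the 5% level. On spread the section says "we assume a conservative standard deviation of 1.71", taken from a cited pilot study. On shape it says "This does assume the actual underlying distribution is normal, but powers for a non-parametric Wilcoxon test". For the step from evaluable to total enrolment it says "we conservatively allow for 20% non-evaluable", which brings the planned recruitment to 337.

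Neither section says whether 1.3 is a mean or a median. Section 14.3 allows transformations where parametric assumptions fail, but only under the secondary and exploratory analyses.

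**The concern.** In a normal model the mean and the median coincide, so section 14.4 never had to choose between them. For a non-negative quantity whose SD exceeds its mean, the distribution must be strongly skewed, and the two separate widely. The signed-rank test also needs symmetry about the null value, and a raw ratio generally does not have it. The calculation therefore describes a variable that the trial will not observe.

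That calculation is the only justification given for 269 evaluable and 337 recruited patients. A reader who relies on the 80% cannot tell what the planned test would do at a PFS ratio of 1.3.

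**Working it through.** **Inputs from the plan (sections 14.2 and 14.4).** Null ratio 1.0, alternative 1.3, SD 1.71, two-sided 5% Wilcoxon test, 80% power, 20% non-evaluable.

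**1. Reproducing the plan's figures.**
- Standardised shift: 0.3 / 1.71 = 0.1754.
- One-sample t-test, two-sided 5%, 80% power: n = 257.
- Wilcoxon efficiency under normality: 257 × π/3 = 269.1. Power at 269 is 79.99%.
- Recruitment: 269 / 0.8 = 336.25, rounded up to 337.
- Simulated signed-rank test on Normal(1.3, 1.71), n = 269: 79%.

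**2. Is the normal model possible here?**
- At the alternative: P(ratio < 0) = Φ(−1.3/1.71) = 22.4%.
- At the null: P(ratio < 0) = Φ(−1.0/1.71) = 27.9%.

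Both should be zero.

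**3. The planned raw-scale test under positive shapes.** The shapes are assumptions. Log-normal parameters, with w = exp(σ²):
- Mean 1.3, SD 1.71: w = 1 + (1.71/1.3)² = 2.730, so σ = 1.002 and the median is 1.3/√2.730 = 0.79.
- Median 1.3, SD 1.71: w(w − 1) = (1.71/1.3)² = 1.730, so w = 1.907, σ = 0.80 and the mean is 1.3 × √1.907 = 1.80.
- Median 1.0, SD 1.71: w(w − 1) = 1.71² = 2.924, so w = 2.282 and σ = 0.91.

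Simulated signed-rank test of (ratio − 1), n = 269, at least 3,000 trials per case:

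| Shape, SD 1.71 | Significant above 1 | Significant below 1 |
|---|---|---|
| Log-normal, mean 1.3 (median 0.79) | under 1% | 9–10% |
| Gamma, mean 1.3 (median 0.67) | under 1% | about 9% |
| Log-normal or gamma, median 1.3 | about 100% | 0% |
| Log-normal, median 1.0 | about 81% | 0% |
| Gamma, median 1.0 | about 86% | 0% |

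A ratio of two independent exponential times with median 1.0 has no finite SD to match to 1.71. There the raw test rejects in about 97% of trials.

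The last two rows are cases of no difference in the median, and the raw test still rejects in most trials. The same test on the log ratio rejects in about 4–5% when the log ratio is symmetric about 0.

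**4. Power on the log scale for a median of 1.3, n = 269.** Power = Φ(ln 1.3 / s × √(269 × 3/π) − 1.96), where s is the SD of the log ratio. The constant is 0.2624 × 16.03 = 4.205. The raw SD implied by a log-normal is 1.3 × exp(s²/2) × √(exp(s²) − 1).

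| s | 4.205/s − 1.96 | Power | Implied raw SD |
|---|---|---|---|
| 0.80 | 3.30 | about 99.9% | 1.7 |
| 1.00 | 2.25 | 98.8% | 2.8 |
| 1.25 | 1.40 | 92% | 5.5 |
| 1.50 | 0.84 | 80% | 11.7 |
| 1.80 | 0.38 | 64.7% | 32.5 |

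For independent exponential times, simulated power on the log scale is about 69–70%.

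**The case against.** The strongest reply has four parts.

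- **The assumption is disclosed and the arithmetic is correct.** This stands. It is not a miscalculation. But disclosing an assumption does not make it possible for this endpoint, and powering for a Wilcoxon test adds only the π/3 factor, which is itself derived under normality.
- **Power may be above 80%.** Section 14.2 reports a median, and with median 1.3 and SD 1.71 rejection is near 100%. A reader might infer from the under-1% figure that the trial is underpowered. The documents do not support that: section 14.4 never calls 1.3 a mean, and the low case needs a median of 0.79, where most patients do worse than on their previous treatment. The power is undetermined, not shown to be lacking. Nor can the near-100% raw-scale figure be taken as reassurance, because the same test rejects about as readily when the median ratio is 1.0.
- **The primary objective is estimation.** Section 2.1.1 does say so. But section 14.2 attaches a test to it, and section 14.4 sizes the trial on that test.
- **A log-SD of 1.5 has no support in the plan.** This also stands. The value is what 269 patients and 80% power imply, and for a log-normal with median 1.3 it means a raw SD near 11.7, against the plan's 1.71. It can serve only as one point in a range.

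**Conclusion.** The 80% claim is an unsupported power statement, not an arithmetic error. It holds for a variable that is below zero 22% of the time, and it does not transfer to a ratio of durations. With SD 1.71 and a skewed positive shape, the chance that the planned raw-scale test shows benefit at 1.3 runs from under 1% to about 100%, depending on whether 1.3 is a mean or a median, and the upper end is not meaningful power.

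The 22% and 28% follow from the plan's own figures. The simulated results rest on the assumed log-normal, gamma and exponential shapes. The SD of 1.71 comes from a source that I could not check.

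A reader might also infer that 269 or 337 must change. Nothing here shows that. If 1.3 is a median and 1.71 is a fair raw SD, a log-normal ratio gives about 99.9% power on the log scale.

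**What to change.** Keep 269 evaluable and 337 recruited, and change two sections together. Changing 14.4 alone would leave it powering a different test from the one in 14.2.

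- **Section 14.2:** state that the two-sided signed-rank test is carried out on the log PFS ratio against 0.
- **Section 14.4:** state that 1.3 is the median ratio, and replace the unconditional 80% with, for example:

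> With 269 evaluable participants, a two-sided 5% signed-rank test on the log PFS ratio has the following power to detect a median ratio of 1.3 against 1.0, by assumed SD of the log ratio: about 99.9% at 0.8, 99% at 1.0, 92% at 1.25, 80% at 1.5 and about 65% at 1.8. If the two times are independent and exponential, power is about 70%. These SDs are assumptions, to be checked against the pilot data on the log scale.

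The value 0.8 is the log-SD implied by a log-normal with median 1.3 and SD 1.71. The value 1.5 should be presented only as the point at which power reaches 80%.

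The cost is a rewording of 14.4 and one sentence in 14.2, with no change in enrolment. The scale of the primary test changes, and the stated power becomes conditional and may look less favourable.
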